4. * Describe how children will be assented to participate in the study (i.e. what will the study team do during the assent process to ensure the child understands what the research involves). Children need to be between 16 and 17 to be able to participate in this study. The conversation about the study (if the child is deemed eligible) will involve the resident/ attending, parent/ legal guardian and the child. The purpose of the study as well as the details will be explained verbally in a language that a child can understand. Emphasis will be laid on voluntary child participation (child has the right to decline participation even if the parent consents).

ID: HM20021396

View: SF2 - Limited English Proficiency

Limited English Proficiency

1. * Describe how Non-English speaking or limited English proficiency participants will be able to communicate with the study staff at enrollment and throughout the study. Include the following information:
- how the initial informed consent process will be handled
 - how the research team plans to interact with LEP participants throughout the conduct of the study
 - whether there will be a qualified interpreter or assistive translational devices available
 - whether the study consent document will be translated or a short form consent document will be used
 - the names of the individuals or professional groups who will provide oral interpretation or written

translation services

Orthodontic treatment is expensive, time consuming and is associated with patient expectations/ responsibilities that need to be communicated very effectively. Traditionally, the Department of Orthodontics treats a high number of Hispanic patients but out of all of our patients, maybe 2% of the total require a spanish speaking staff member. We have provided the resumes of staff (who would provide translation services at VCU and at [name] offices) attesting their fluency in Spanish. [name] office will not enrol LEP participants due to lack of resources. The SoD do not have MAARTI or blue phones and traditionally rely on staff to do this service for the patients.

We intend to use the short form consent because we do not anticipate recruiting more than 5% of LEP subjects. In the event, we reach 3 LEP participants (4%), we would submit a translated consent document as an amendment for IRB review and approval prior to further enrollment.

2. * Describe any additional risks or harms to the individual because of their limited English proficiency and how these will be minimized.

No other risks or harms will occur to participants with LEP.

3. If an interpreter or translator will be involved in the study, upload documentation verifying qualifications.

ID: HM20021396

View: SF2 - Populations with Special Considerations Section Complete

Populations with Special Considerations Section Complete

Protocol Progress:

? INITIAL SETUP

? BACKGROUND, RATIONALE & GOALS

? RESEARCH PLAN

? CONSENT PLAN

? RISKS, PRIVACY & CONFIDENTIALITY

? POPULATIONS WITH SPECIAL CONSIDERATIONS

? INSTITUTIONAL REQUIREMENTS

? DOCUMENTS

Click Continue below to go to the next section

ID: HM20021396

View: SF2 - Study Funding

Study Funding

1. * Have you applied for funding: Yes No**2. Is this study already funded:** Yes No**3. * Select all funding sources for this study (pending or awarded):** Industry Direct Federal Indirect Federal State/Local Government Non-Profit - Sponsored Project Non-Profit - Gift Internal Grant

Investigator/Departmental Funds

None

Other

4. Select all related proposals:

RAMS-SPOT ID# (FP/PT/PD#)	Sponsor	PI Title	Status	Start	End
---------------------------	---------	----------	--------	-------	-----

There are no items to display

ID: HM20021396

View: SF2 - Types of Sites

Types of Sites

VCU Site Information

1. * Select all VCU sites that will be utilized in this study:

- Children's Hospital of Richmond at VCU
- Clinical Research Services Unit (CRSU)
- Massey Cancer Center
- VCU Health Community Memorial Hospital
- VCU Medical Center
- VCU Monroe Park Campus
- VCU Qatar
- Other VCU Site

Non-VCU Site Information

Non-VCU sites should be selected whenever any of the following situations apply::

- a) Non-VCU sites that will be collaborating on a VCU-led study
- b) Non-VCU sites that will be deferring to the VCU IRB for IRB review
- c) Non-VCU sites where VCU investigators will be overseeing study interventions or interactions
- d) Non-VCU sites/locations where VCU investigators will conduct study activities

2. * Select any of the following non-VCU sites utilized in this study:

- McGuire VAMC
- Foreign Sites
- Other Non-VCU Sites
- No Non-VCU Sites

3. * Is this a multi-center study being led by VCU?

Yes No

4. * List all Non-VCU sites and locations:

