The 2009 [name] et al study reported that maxillary lateral incisors were the teeth that most commonly required extrusion. This was a particularly inaccurate movement with aligners due to the difficulty of the aligners grasping the teeth and pulling them vertically. Boyd described absolute extrusion as being particularly challenging and advocated for the use of a mid-treatment correction such as elastics attached to a button bonded to the facial aspect, or combining extrusion with more predictable movements like lingual constriction or retroclination. Orthodontists have reported 70% to 80% of their aligner patients needing some level of mid-treatment intervention or refinement series to accomplish the goals of the treatment plan.

Though more recent studies have reported improvements in the predictability of most aligner movements, the measured outcomes still fall short of the anticipated changes. Because of the particular difficulties involved with controlling maxillary lateral incisor vertical positioning with aligners, there are many differing expert opinions on how lateral incisor extrusion should be accomplished. Glaser described in his 10 commandments of attachment design, that 4 mm wide gingivally beveled attachments on the maxillary lateral incisors would aid in more accurate extrusive movement. Gomez et al described the initial force systems generated by plastic aligners with and without attachments. They found that attachments created the force systems necessary to bodily tooth movement. Additionally, in a guest editorial in *The Angle Orthodontist* in 2008, Brezniak claimed that attachments added retentiveness and that extrusion was a difficult movement without attachments due to the clear aligners' tendency to concentrate force in the incisal portion of the teeth. No studies to date have specifically evaluated the challenging movement of maxillary lateral extrusion prospectively, comparing differences in attachment design and determining differences in their effectiveness.

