Based on data from prior publications, the common standard deviation for extrusion was assumed to be 1.25. When the sample size is 15, a one-way repeated measures analysis of variance with a 0.05 significance level will have 80% power to detect a difference in means across the 4 groups of the repeated measures factor characterized by an effect size of 0.199 (based on a Variance of means, $V = \frac{(\sigma^2 - \rho^2)}{M}$, of 0.156, a standard deviation at each level of 1.25, and a between level correlation, ρ , of 0.5).

Increasing the sample size to 20 per group would have power to detect an effect size of 0.146 and variance of means of 0.114. These estimates reflect small effect sizes 15 and therefore would be able to detect clinically meaningful differences in the extrusion of the 4 attachments. Sample size calculations estimated with nQuery v8.5.2 (Statistical Solutions Ltd 2020).

4. * List the study inclusion criteria:

- (1) Patients 16 years or older to be treated with either Comprehensive Invisalign or Invisalign Teen,
- (2) Maxillary lateral incisor requiring 0.3 mm or more extrusion (as determined by ClinCheck),
- (3) Maxillary arch with less than 6 mm of crowding or spacing,
- (4) All teeth present and fully erupted (excluding third molars).

5. * List the study exclusion criteria:

- (1) Presence of anterior crossbite
- (2) Any missing teeth in the maxillary arch
- (3) Treatment plan includes surgery or extraction of any maxillary teeth,
- (4) Maxillary lateral incisors with pathology or large restorations (crowns)
- (5) Maxillary lateral incisors have a less than 0.3 mm of extrusion prescribed in the Tooth Movement Table on the Invisalign ClinCheck

6. * Will individuals with limited English proficiency be included in or excluded from this research?

Included

- Excluded - safety concerns if participants are unable to communicate with the study team
- Excluded - instruments/measures only validated in English
- Excluded - no prospect of direct benefit to individual participants
- Excluded - minimal risk study
- Excluded - lack of budget/resources for translation and interpretation [provide an explanation in next question]
- Excluded - other reason [provide an explanation in next question]

7. Justify the inclusion and exclusion criteria if you are either targeting, or excluding, a particular segment of the population / community. Provide a description of the group/organization/community and provide a rationale.

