a. Routine clinical practice: All potential patients seeking orthodontic treatment will have an initial consultation appointment with the orthodontist. At this appointment, the orthodontist will have an opportunity to assess patient needs/ expectations as well as conduct an examination to present viable treatment options to the patient. All patients will also have their teeth and gums scanned by an intraoral scanner. This information is sent to Align Technology whose proprietary software (ClinCheck) is used to design and engineer a sequential set of trays that would progressively move teeth to their ideal positions in the mouth. ClinCheck software also provides the quantitative estimate of the magnitude of tooth movement required (in tenths of mm) as well as its direction (in degrees). Together, this information is used to design the clear aligners.

b. Study related screening:

During this consultation appointment, the patients will be evaluated to see if they meet the stated exclusion criteria (missing teeth in maxillary arch; lateral incisors with pathology/ restorations, treatment plan include extractions, presence of anterior cross bite, need for maxillary lateral incisor extrusion) to screen out ineligible study participants.

All patients who do not meet the exclusion criteria will be considered potential study participants and will be informed of the study and requested to participate and consent obtained. Their teeth and gums will be scanned as indicated under routine clinical care and the final inclusion will be determined based on the report generated by ClinCheck (>0.3mm lateral incisor extrusion and <6mm crowding). The time gap between intraoral scanning and generation of ClinCheck is a few days and getting the consent for all non-excluded participants is proposed out of respect for patient/ doctor's time because it precludes a need for a separate appointment (just to get consent) and improves efficiency.

It will be explained to the patient that they could be excluded from the study if analysis of ClinCheck software data indicates their ineligibility (required lateral incisor extrusion <0.3mm and crowding >6mm). Such patients would be considered screening failures.

5. * Does this study have a separate protocol document (i.e. a multisite or sponsor's protocol) that contains a detailed description of the study's methodology?

Yes

No

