During the scheduled appointment for the delivery of aligners, the patients will be instructed on how to properly place and remove aligners and their maintenance. Patients will be instructed to wear each aligner for a minimum of 22 hours a day for 7 days. Participants will verbally confirm compliance at each appointment. At the end of a series of 20-25 aligners, another intraoral scan will be taken and sent to Align Technologies to determine the final positions of the teeth. Comparison of initial and final positions (using Geomagic software) will be done to assess the efficacy of different types of attachments in lateral incisor extrusion.

Once the teeth are in desired positions, the treating orthodontist will remove the attachment (<6 months).

3.

Research related interventions include:

- a. random assignment of the specific type of attachment on lateral incisor;
- b. treating orthodontist placing the corresponding order in the prescription with Align Technology;
- c. delivery of attachments and aligners to the study participants
- d. Superimposition of final and initial positions of lateral incisors: Two superimpositions will be completed. The pretreatment model will be superimposed with the predicted final model to establish the predicted movement of the maxillary lateral incisors. The pretreatment model will be superimposed with the posttreatment model to establish the actual movement of the maxillary lateral incisor. The actual and predicted movement values will be calculated by the GeoMagic software. The amount of extrusion for the lateral incisors will be analyzed in increments of 0.1 mm.

Sample size: 80 maxillary lateral incisors with at least 20 teeth per study group. Randomization will occur at the level of individual lateral incisor tooth.

Study Duration: Patients will be evaluated only after the first series of aligners (20-25). Each set of aligners would be worn for a week and the study would span 20 - 25 weeks.

7. * The IRB only reviews research activities, so indicate which of the study activities are:

- **Being performed exclusively for research purposes (i.e. they would not otherwise be done apart from this study) VERSUS.**
- **Alterations of routine activities/procedures (e.g. the study is altering the timing, frequency, method, location, amount, etc.) VERSUS.**

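### The planned angular movement of each tooth, available from ClinCheck before treatment, is not used in the attachment comparison, at a modest cost in precision

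*Combined protocol and SAP*

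**What the plan says.** **Background, Rationale and Goals, Q1.** One cited expert is reported as describing "absolute extrusion as being particularly challenging" and as advising either a mid-treatment correction, such as elastics to a bonded button, "or combining extrusion with more predictable movements like lingual constriction or retroclination".

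**Study Population, Q4 and Q5.** Extrusion eligibility is in millimetres only. Inclusion criterion 2 reads "Maxillary lateral incisor requiring 0.3 mm or more extrusion (as determined by ClinCheck", and exclusion criterion 5 is its mirror image, read from the ClinCheck Tooth Movement Table. Neither refers to a planned change of inclination.

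**Study Procedures, Q4.** At the planning stage, ClinCheck supplies a quantitative estimate of the "magnitude of tooth movement required (in tenths of mm) as well as its direction (in degrees".

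**Study Procedures, Q6, and Data Confidentiality and Storage, Q9.** Individual lateral incisors are randomised in computer-generated blocks of 4. No stratification factor is given.

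**Study Procedures, Q6.** For each study tooth, the pretreatment model is "superimposed with the predicted final model to establish the predicted movement of the maxillary lateral incisors", and a second superimposition gives the actual movement. The stated analysis variable is one-dimensional: "The amount of extrusion for the lateral incisors will be analyzed in increments of 0.1 mm".

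**Study Population, Q3.** The only statistical model named is the one-way repeated-measures ANOVA behind the sample size, with attachment group as its single factor. The secondary objective concerns the predicted three-dimensional position, but no angular measure or method is described for it.

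**The concern.** A prescription of, say, 0.5 mm does not show whether a tooth is to be pulled straight down or extruded while it is tipped back. The background gives a reason to expect these two situations to respond differently, and the trial asks which attachment gives the more predictable extrusion. If they do respond differently, the mix of teeth adds variance to the outcome that a pretreatment measurement could explain.

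Two things are at stake. An unadjusted comparison is less precise than it could be. And with 20 teeth per arm the mix will often differ visibly between arms by chance. Without a rule set in advance, the investigators would then have to decide whether to adjust after seeing the imbalance.

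**Working it through.** **Inputs from the plan (Study Population, Q3):** SD 1.25 (unit not stated), between-level correlation ρ = 0.5, M = 4 attachments, α = 0.05, n = 20 per group with variance of means V = 0.114. The comparison case is n = 15 with V = 0.156.

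**Assumed, because the documents give neither:** the share R² of outcome variance explained by planned inclination change (0.10 to 0.20), and the proportion p of teeth with planned retroclination (0.2 to 0.5).

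**Step 1. Reproduce the plan's figures.** Effect size = V / [SD²(1 − ρ)], noncentrality λ = n·M·effect size, with M − 1 and (M − 1)(n − 1) degrees of freedom. Here SD²(1 − ρ) = 1.5625 × 0.5 = 0.78125.

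- n = 15: 0.156 / 0.78125 = 0.1997 (plan: 0.199); λ = 11.98 on 3 and 42 df; power 80.0%.
- n = 20: 0.114 / 0.78125 = 0.1459 (plan: 0.146); λ = 11.67 on 3 and 57 df; power 79.98%.

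The stated figures reproduce and are not in dispute here.

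**Step 2. Effect of adjustment on power.** A covariate explaining R² reduces the residual SD to 1.25·√(1 − R²) and divides λ by (1 − R²). Teeth are randomised individually and a patient has at most two maxillary lateral incisors, so the independent-groups version is shown as well: λ = n·M·V / SD² = 20 × 4 × 0.114 / 1.5625 = 5.84 on 3 and 76 df (75 with the covariate).

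| Assumed R² | Residual SD | λ, plan's formula | Power | λ, independent groups | Power |
|---|---|---|---|---|---|
| 0 (no covariate) | 1.25 | 11.67 | 80% | 5.84 | 48% |
| 0.10 | 1.19 | 12.97 | 84% | 6.49 | 53% |
| 0.20 | 1.12 | 14.59 | 89% | 7.30 | 58% |

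In the plan's formula ρ is held at 0.5 and no degree of freedom is deducted; deducting one changes none of the rounded values. In equivalent teeth, 80/(1 − R²) − 80 gives about 9 extra at R² = 0.10 and 20 at R² = 0.20.

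**Step 3. Chance imbalance with 20 teeth per arm.** The SE of the difference in share between two arms is √[2p(1 − p)/20]. The probabilities come from simulating four independent binomial arms of 20.

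| Assumed p | SE of difference (points) | Some pair of arms ≥ 20 points apart | ≥ 30 points apart |
|---|---|---|---|
| 0.2 | 12.6 | 50% | 12% |
| 0.3 | 14.5 | 62% | 22% |
| 0.5 | 15.8 | 68% | 30% |

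A visible difference in mix somewhere among the arms is therefore likely.

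**Step 4. What that imbalance does to the result.** With no attachment effect, the expected gap between the highest and lowest of four arm means of 20 teeth is 0.46 SD. After adjustment it is 0.46·√(1 − R²): 0.44 SD at R² = 0.10 and 0.41 SD at R² = 0.20, a reduction of about 5% to 11%. This is the variance reduction of Step 2 seen from another side. The two should not be added together.

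**The case against.** The strongest reply is that randomisation already deals with this. It does in one sense: allocation is random, so chance imbalance in any baseline feature is part of ordinary sampling error and is covered by the 0.05 level and the assumed SD. A reader might infer from Step 3 that the trial is biased, or that imbalance adds a spurious attachment effect on top of random error. The documents do not support that, and Step 4 shows that adjustment shrinks the null spread only modestly.

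A reader might also infer that the plan itself declares the two kinds of extrusion to differ strongly in predictability. It does not. The background reports one expert's opinion and gives no measured difference; the words *more predictable* are attached to the accompanying movements, not to the combined extrusion. It also says that expert opinions on achieving lateral incisor extrusion differ. *Plausible predictor* is as far as the text goes.

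Three further points stand in part:

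- The research question concerns lateral incisor extrusion in general, so including both kinds of tooth is a legitimate target and not an error.
- The ANOVA is named for the power calculation, and no analysis section gives any covariate. The omission is therefore not shown to be a deliberate decision about inclination.
- ClinCheck's output is described as direction in degrees, so availability of inclination specifically is inferred. The superimposition of the pretreatment and predicted models is a second possible source.

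None of this removes the point. A baseline covariate is chosen on prior clinical reasoning, which the plan supplies, and using it is cheap.

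**Conclusion.** The point holds as an inexpensive gain in precision, not as a flaw that invalidates the comparison. The plan gives a reason to expect the planned accompanying movement to matter and describes a pretreatment source of angular information. It does not use that information in eligibility, in allocation or in the one-factor model it names.

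The gain is modest and depends wholly on the assumed R². At 0.10 to 0.20, power rises by about 4 to 9 percentage points under the plan's formula, and by about 5 to 10 if the four groups are independent. If R² is near zero there is no gain, and the loss is one of about 76 residual degrees of freedom. The separate benefit, which does not depend on R², is that the adjustment is fixed before results are seen and readers can judge whether the arms were alike on this feature.

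**What to change.** Pre-specify the planned inclination change (degrees) of each study tooth as a baseline covariate in the attachment comparison, and tabulate it by arm. Take the value from the ClinCheck version fixed before the assigned design is released to the treating orthodontist, or from the pretreatment-to-predicted superimposition of that same version. A later version could reflect the assigned design and would no longer be a baseline value.

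The cost is one value per tooth from records the study already obtains, and one model degree of freedom. There is no added patient contact and no change to treatment.

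The plan should state two limits. A linear term in degrees does not capture lingual constriction, the other accompanying movement named in the background. And with 20 teeth per arm the trial is not powered for subgroups by type of extrusion, so any such split should be descriptive or exploratory only.

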Costs to Participants

1. * Select all categories of costs that participants or their insurance companies will be responsible for:

- Participants will have no costs associated with this study
- Study related procedures that would be done under standard of care
- Study related procedures not associated with standard of care
- Administration of drugs / devices
- Study drugs or devices
- Other

ID: HM20021396

View: SF2 - Compensation

Compensation

1. * Describe any compensation that will be provided including:
 1. total monetary amount
 2. type (e.g., gift card, cash, check, merchandise, drawing, extra class credit)
 3. how it will be disbursed

Every lateral incisor that requires extrusion and qualifies for the study will be compensated with a \$50 gift card. The compensation will be distributed to study participants in person when they complete the second intraoral scan at the end of their initial series of clear aligners. Since there are two lateral incisors, a study participant's potential compensation can be \$100 if both their lateral incisors qualify for the study.

2. If compensation will be pro-rated, explain the payment schedule.
Compensation will not be pro-rated.

3. * Will Social Security Numbers be collected for compensation purposes only?

Yes
 No

ID: HM20021396

View: SF2 - Research Plan Complete

Research Complete

Protocol Progress:

- ? INITIAL SETUP
- ? BACKGROUND, RATIONALE & GOALS
- ? RESEARCH PLAN
- ? CONSENT PLAN
- ? RISKS, PRIVACY & CONFIDENTIALITY
- ? POPULATIONS WITH SPECIAL CONSIDERATIONS
- ? INSTITUTIONAL REQUIREMENTS
- ? DOCUMENTS

Click Continue below to go to the next section

ID: HM20021396

View: SF2 - Consent Process

Consent Process

1. * List all consent groups:

Group Types	Waivers	Roles	Roles - Other	Consent	Coercion	Decision	Re-Consent

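### The only analysis the plan names, a four-level repeated measures ANOVA, cannot be fitted because no patient can carry more than two of the four attachment designs

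*Combined protocol and SAP*

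**What the plan says.** The statistical text is confined to SF2 - Study Population, item 3. It takes "a one-way repeated measures analysis of variance with a 0.05 significance level" and claims "80% power to detect a difference in means across the 4 groups of the repeated measures factor" when the sample size is 15. The inputs are an SD of 1.25 ("the common standard deviation for extrusion was assumed to be 1.25"), an effect size of 0.199, a variance of means of 0.156 and "a between level correlation, ρ , of 0.5". At 20 per group the detectable effect size becomes 0.146 and the variance of means 0.114.

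The design is described elsewhere:

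- SF2 - Study Procedures, item 6 sets 80 teeth, at least 20 per design, and states: "Randomization will occur at the level of individual lateral incisor tooth". On the comparison of designs it says only that initial and final tooth positions will be compared; it gives no test or model.
- SF2 - Compensation, item 1 doubles the payment "if both their lateral incisors qualify for the study", so a patient may contribute one tooth or two.
- SF2 - Data Confidentiality and Storage, item 9 assigns each participant, not each tooth, to one of the four designs, in blocks of four. It builds the participant code from enrolment order and the attachment type received.

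**The concern.** A one-way repeated measures ANOVA on four levels compares designs within a subject, so each subject must be observed under all four. A patient with two upper lateral incisors cannot be. The model in the sample-size answer therefore does not describe the data the trial will produce, and nothing else in the document fills the gap.

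Two things are at stake. The analysis of the main question is left open and could be chosen after the data are seen. The stated 80% power belongs to a design in which every comparison between attachments is free of between-patient variation, which this trial cannot achieve.

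**Working it through.** **Inputs from the document.** M = 4 designs, SD = 1.25 (SD² = 1.5625), ρ = 0.5, alpha 0.05, V = 0.156 at n = 15 and V = 0.114 at n = 20, 80 teeth, blocks of four.

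**1. Reproduce the plan's figure.** For a repeated measures ANOVA, effect size = V/[SD²(1−ρ)], noncentrality λ = nMV/[SD²(1−ρ)], and df = M−1 and (n−1)(M−1).

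- n = 15: effect size 0.156/0.78125 = 0.1997; λ = 15 × 4 × 0.156/0.78125 = 11.98; df 3 and 42; power 80.0%.
- n = 20: effect size 0.114/0.78125 = 0.1459; λ = 20 × 4 × 0.114/0.78125 = 11.67; df 3 and 57; power 80.0%.

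Both match. In this formula n counts subjects who each supply all four designs, so the model meant really is the within-subject one.

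**2. Compare with the design.** Tooth-level randomisation gives a patient one or two designs. Participant-level assignment gives exactly one. Under neither wording can anyone have four.

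**3. Power for the same V with teeth as they will occur.** Treat 0.5 as the correlation between two teeth of one patient (an assumption; the plan gives it as a between-level correlation).

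- One tooth per patient: λ = 80 × 0.114/1.5625 = 5.84; df 3 and 76; power 48%. Reaching 80% would need 39 teeth per group (156 in all), or V = 0.224 at 20 per group.
- 40 two-tooth patients, different designs on the two teeth, all design pairs equally frequent: two thirds of the information on designs is within patients and one third between. λ = 5.84 × [(2/3)/(1−0.5) + (1/3)/(1+0.5)] = 5.84 × 1.556 = 9.08; power 66–69% for denominator df from 37 to 76.
- 40 two-tooth patients, same design on both teeth: λ = 5.84/(1+0.5) = 3.89; df 3 and 36; power 32%.

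The second case depends strongly on ρ: λ = 7.06 and power 54–57% at ρ = 0.3; λ = 14.1 and power 86–88% at ρ = 0.7.

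**4. What a one-way ANOVA that ignored patients would do.** Simulation of 80 teeth at ρ = 0.5, with 4,000 runs for type I error and interval coverage and 2,000 for power at V = 0.114. The comparator is generalised least squares with ρ treated as known; its type I error was 4.0–4.6%.

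| Allocation | Patients | Type I, patients ignored | 95% interval coverage | Power, patients ignored | Power, patient-correlated model |
|---|---|---|---|---|---|
| Tooth, blocks of 4 | 40 two-tooth | 2.4% | 96.8% | 45% | 70% |
| Tooth, blocks of 4 | 20 two-tooth, 40 one-tooth | 3.9% | 95.7% | 47% | 60% |
| Tooth, no blocks | 40 two-tooth | 5.3% | 94.8% | 50% | 62% |
| Patient | 40 two-tooth | 16.7% | 88.5% | 56% (inflated) | 32% |
| Patient | 20 two-tooth, 40 one-tooth | 9.8% | 91.8% | 52% (inflated) | 39% |
| Tooth, blocks of 4 | 80 one-tooth | 5.1% | 95.0% | 49% | 49% |

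For 40 two-tooth patients and ρ from 0.3 to 0.7, type I error runs from 3.6% to 1.6% under tooth-level blocks and from 11.3% to 21.3% under patient-level allocation.

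**5. The proposed replacement.** A separate simulation (3,000 runs per cell) fitted a REML model with patient correlation. Type I error was 5.0–5.1%, except 6.1% for 27 two-tooth plus 26 one-tooth patients under tooth-level allocation, where an approximate denominator df of 55 was used. Power was 67–69% with 40 two-tooth patients and 62–64% in the 27 + 26 mix. Kenward-Roger degrees of freedom are recommended because of the 6.1%; they were not themselves simulated.

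**The case against.** The ANOVA appears only in answer to a sample-size question, so it may be read as a planning device and not a commitment. That is fair, but it leaves the document with no stated analysis at all.

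A reader might infer that the sponsor will analyse 80 teeth as independent and so report wrong p-values. The document does not say so. No such fallback is named, and a correlation of 0.5 in the planning text points away from ignoring patients. Nor would that analysis always be wrong: it is valid with one tooth per patient, which a maximum of 80 subjects for 80 teeth does not exclude, and close to 5% with unblocked tooth-level allocation. Under tooth-level blocks of four it is conservative. The 10–17% error rates need both teeth to get the same design, which follows from the participant-level wording and contradicts the tooth-level sentence.

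A reader might also infer that the trial cannot be analysed. That goes too far: only the complete-row form of repeated measures ANOVA fails, and a mixed model accepts one or two teeth per patient.

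Finally, a coded participant identifier is already planned for every analysis record. That stands, but the code is built on one attachment type per participant and does not obviously accommodate a patient whose two teeth carry different designs.

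**Conclusion.** The mismatch is certain and needs no assumption: the one named test requires four designs per subject, and the design yields at most two. It is an error in the text as written and should be corrected before analysis.

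The sizes are conditional. They assume ρ = 0.5 between a patient's teeth, no dropout, and shares of two-tooth patients chosen for illustration. The tooth-level figures also assume that a patient's two teeth take consecutive places in the randomisation list. On that basis the stated 80% is not supported in any scenario at ρ = 0.5: power runs from about 32% to about 70% according to allocation unit and teeth per patient. It would pass 80% only with a higher correlation and nearly all patients contributing two differently treated teeth. The harm from ignoring patients is a risk the plan leaves open, not something it proposes.

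**What to change.** 1. Replace the named test with a linear mixed model on teeth: fixed effect for design (four levels), random intercept for patient, REML with Kenward-Roger degrees of freedom, and a 3-df test of design at 0.05. Keep all teeth, including those of one-tooth patients.
2. State that the coded identifier links both teeth of a patient in the analysis file, with design recorded per tooth. Settle this before the linking key is destroyed, because the pairing may not be recoverable afterwards.
3. Reconcile the allocation unit between SF2 - Study Procedures, item 6 and SF2 - Data Confidentiality and Storage, item 9.
4. Restate the power on the mixed model, with an explicit share of two-tooth patients and a range for ρ.

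Items 1 to 3 cost wording and one coded variable, with no extra visits or scans. Item 4 may cost more. The mixed model uses the data better but does not restore 80% at ρ = 0.5, so the sponsor must either accept a larger detectable difference (V = 0.224 with one tooth per patient and 20 per group) or plan more teeth (156 on the same basis, which would exceed the stated maximum of 80 subjects).
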